5.4.5.6 Stable Disease/No Change

Does not meet criteria for any of the categories above.

[REDACTED]

[REDACTED]

[REDACTED]

[REDACTED]	[REDACTED]	[REDACTED]	[REDACTED]	[REDACTED]
[REDACTED]	[REDACTED]	[REDACTED]	[REDACTED]	[REDACTED]
		[REDACTED]	[REDACTED]	
		[REDACTED]	[REDACTED]	
	[REDACTED]	[REDACTED]	[REDACTED]	
		[REDACTED]	[REDACTED]	
	[REDACTED]	[REDACTED]	[REDACTED]	
		[REDACTED]	[REDACTED]	
	[REDACTED]	[REDACTED]	[REDACTED]	
		[REDACTED]	[REDACTED]	
[REDACTED]	[REDACTED]	[REDACTED]	[REDACTED]	[REDACTED]
		[REDACTED]	[REDACTED]	
	[REDACTED]	[REDACTED]	[REDACTED]	
		[REDACTED]	[REDACTED]	
[REDACTED]	[REDACTED]	[REDACTED]	[REDACTED]	[REDACTED]
		[REDACTED]	[REDACTED]	
	[REDACTED]	[REDACTED]	[REDACTED]	
[REDACTED]	[REDACTED]	[REDACTED]	[REDACTED]	[REDACTED]
[REDACTED]	[REDACTED]	[REDACTED]	[REDACTED]	[REDACTED]
[REDACTED]	[REDACTED]	[REDACTED]	[REDACTED]	[REDACTED]
[REDACTED]	[REDACTED]	[REDACTED]	[REDACTED]	[REDACTED]
[REDACTED]	[REDACTED]	[REDACTED]	[REDACTED]	[REDACTED]
[REDACTED]	[REDACTED]	[REDACTED]	[REDACTED]	[REDACTED]
[REDACTED]	[REDACTED]	[REDACTED]	[REDACTED]	[REDACTED]

[REDACTED]		[REDACTED]		
[REDACTED]	[REDACTED]	[REDACTED]	[REDACTED]	[REDACTED]
[REDACTED]	[REDACTED]	[REDACTED]	[REDACTED]	[REDACTED]
[REDACTED]	[REDACTED]	[REDACTED]	[REDACTED]	[REDACTED]
[REDACTED]	[REDACTED]	[REDACTED]	[REDACTED]	[REDACTED]
[REDACTED]	[REDACTED]	[REDACTED]	[REDACTED]	[REDACTED]

[REDACTED]

[REDACTED]

[REDACTED]

[REDACTED]

[REDACTED]

[REDACTED]

5.8 Outcomes Research Assessments

5.8.1 HRQoL Assessments

To assess the impact of treatment, subject's quality of life will be measured using 3 validated QoL instruments:

[REDACTED] and the Brief Pain Inventory- Short Form (BPI-SF).

All three questionnaires will be administered per the schedule in [Table 5.1-1](#), [Table 5.1-2](#), and [Table 5.1-3](#). Subjects should fill out the questionnaire prior to any study-related procedures, treatment or clinician assessment in order to prevent these variables from influencing QoL results. Non-English speaking subjects will complete the questionnaire using validated language transitions developed and recommended for each instrument.

The BPI-SF is a 15-item ([Appendix 5](#)) instrument designed to assess pain in patients with cancer and other diseases.^{50,51} It measures the pain intensity (5-item sensory dimension), and it also includes questions to measure the interference of pain in the patient's daily life, including general activity, mood, ability to walk, normal work both outside the home and housework, relations to other people, sleep, as well as enjoyment of life (7-item reactive dimension).⁵² In multiple myeloma patients, significant associations were found between pain intensity measured by the BPI-SF and mood disturbance scores. As pain interference increased, so did levels of mood disturbance. A joint predictive model explained 74.6% of the variability in total QOL scores.⁵³ The BPI-SF has demonstrated both reliability and validity across cultures and languages, and has been used to study the effectiveness of pain treatment.⁵⁰ A score of 6 on a scale of 0 to 10 on any single item is generally considered to be clinically significant.⁵⁴

Pre-testing was carried out in the UK, Norway, Sweden, Denmark, and Germany. Field testing of the module has been conducted in a range of Phase 3 trials.⁵⁵ The module has been validated in a large number of languages (see www.eortc.be/home/qol).

5.9 Other Assessments

Not applicable.

6 ADVERSE EVENTS

An *Adverse Event (AE)* is defined as any new untoward medical occurrence or worsening of a pre-existing medical condition in a patient or clinical investigation subject administered an investigational (medicinal) product and that does not necessarily have a causal relationship with this treatment. An AE can therefore be any unfavorable and unintended sign (including an abnormal laboratory finding, for example), symptom, or disease temporally associated with the use of investigational product, whether or not considered related to the investigational product.

Adverse events can be spontaneously reported or elicited during open-ended questioning, examination, or evaluation of a subject. (In order to prevent reporting bias, subjects should not be questioned regarding the specific occurrence of one or more AEs.)

6.1 Serious Adverse Events

A *serious AE (SAE)* is any untoward medical occurrence that at any dose:

- results in death
- is life-threatening (defined as an event in which the subject was at risk of death at the time of the event; it does not refer to an event which hypothetically might have caused death if it were more severe)
- requires inpatient hospitalization or causes prolongation of existing hospitalization (see **NOTE** below)
- results in persistent or significant disability/incapacity
- is a congenital anomaly/birth defect
- is an important medical event (defined as a medical event(s) that may not be immediately life-threatening or result in death or hospitalization but, based upon appropriate medical and scientific judgment, may jeopardize the subject or may require intervention [eg, medical, surgical] to prevent one of the other serious outcomes listed in the definition above.) Examples of such events include, but are not limited to, intensive treatment in an emergency room or at home for allergic bronchospasm; blood dyscrasias or convulsions that do not result in hospitalization.) Potential drug induced liver injury (DILI) is also considered an important medical event (See [Section 6.6](#) for the definition of potential DILI).

Suspected transmission of an infectious agent (eg, any organism, virus or infectious particle, pathogenic or non-pathogenic) via the study drug is an SAE.

Although pregnancy, overdose, cancer, and potential DILI are not always serious by regulatory definition, these events must be handled as SAEs for data transmission purposes (See [Section 6.1.1](#) for reporting pregnancies).

NOTE:

The following hospitalizations are not considered SAEs in BMS clinical studies:

- a visit to the emergency room or other hospital department < 24 hours, that does not result in admission (unless considered "important medical event" or event life threatening)

- elective surgery, planned prior to signing consent
- admissions as per protocol for a planned medical/surgical procedure
- routine health assessment requiring admission for baseline/trending of health status (eg, routine colonoscopy)
- medical/surgical admission for purpose other than remedying ill health state and was planned prior to entry into the study. Appropriate documentation is required in these cases
- admission encountered for another life circumstance that carries no bearing on health status and requires no medical/surgical intervention (eg, lack of housing, economic inadequacy, care-giver respite, family circumstances, administrative).
- Admission for administration of anticancer therapy in the absence of any other SAEs (applies to oncology protocols).

6.1.1 Serious Adverse Event Collection and Reporting

Sections 5.6.1 and 5.6.2 in the Investigator Brochure (IB) represent the Reference Safety Information to determine expectedness of serious adverse events for expedited reporting. Following the subject's written consent to participate in the study, all SAEs, whether related or not related to study drug, must be collected, including those thought to be associated with protocol-specified procedures. All SAEs must be collected that occur during the screening period and within 60 days of discontinuation of dosing or within 30 days of the last visit for screen failures.

The investigator must report any SAE that occurs after these time periods and that is believed to be related to study drug or protocol-specified procedure.

An SAE report must be completed for any event where doubt exists regarding its seriousness.

If the investigator believes that an SAE is not related to study drug, but is potentially related to the conditions of the study (such as withdrawal of previous therapy or a complication of a study procedure), the relationship must be specified in the narrative section of the SAE Report Form.

SAEs, whether related or not related to study drug, and pregnancies must be reported to BMS (or designee) within 24 hours of awareness of the event. SAEs must be recorded on the SAE Report Form; pregnancies on a Pregnancy Surveillance Form (electronic or paper forms). The preferred method for SAE data reporting collection is through the eCRF. The paper SAE/pregnancy surveillance forms are only intended as a back-up option when the eCRF system is not functioning. In this case, the paper forms are to be transmitted via email or confirmed facsimile (fax) transmission to:

SAE Email Address: Refer to Contact Information list.

SAE Facsimile Number: Refer to Contact Information list.

For studies capturing SAEs through electronic data capture (EDC), electronic submission is the required method for reporting. In the event the electronic system is unavailable for transmission,

paper forms must be used and submitted immediately. When paper forms are used, the original paper forms are to remain on site.

SAE Telephone Contact (required for SAE and pregnancy reporting): Refer to Contact Information list.

If only limited information is initially available, follow-up reports are required. (Note: Follow-up SAE reports must include the same investigator term(s) initially reported.)

If an ongoing SAE changes in its intensity or relationship to study drug or if new information becomes available, the SAE report must be updated and submitted within 24 hours to BMS (or designee) using the same procedure used for transmitting the initial SAE report.

All SAEs must be followed to resolution or stabilization.

6.2 Nonserious Adverse Events

A *nonserious adverse event* is an AE not classified as serious.

6.2.1 Nonserious Adverse Event Collection and Reporting

The collection of nonserious AE information should begin at initiation of study drug. Nonserious AE information should also be collected from the start of a placebo lead-in period or other observational period intended to establish a baseline status for the subjects.

Nonserious AEs should be followed to resolution or stabilization, or reported as SAEs if they become serious (see [Section 6.1.1](#)). Follow-up is also required for nonserious AEs that cause interruption or discontinuation of study drug, or those that are present at the end of study treatment as appropriate. All identified nonserious AEs must be recorded and described on the nonserious AE page of the CRF (paper or electronic).

Completion of supplemental CRFs may be requested for AEs and/or laboratory abnormalities that are reported/identified during the course of the study.

6.3 Laboratory Test Abnormalities

The following laboratory abnormalities should be captured on the nonserious AE CRF page or SAE Report Form (paper or electronic) as appropriate:

- Any laboratory test result that is clinically significant or meets the definition of an SAE
- Any laboratory abnormality that required the subject to have study drug discontinued or interrupted
- Any laboratory abnormality that required the subject to receive specific corrective therapy.

It is expected that wherever possible, the clinical, rather than the laboratory term would be used by the reporting investigator (eg, anemia versus low hemoglobin value).

6.4 Pregnancy

If, following initiation of the investigational product, it is subsequently discovered that a study subject is pregnant or may have been pregnant at the time of investigational product exposure,

including during at least time to washout (90 days) plus one ovulatory cycle (30 days) for a total of 120 days, or plus one spermatogenesis cycle (90 days) for a total of 180 days after product administration, the investigational product will be permanently discontinued in an appropriate manner (eg, dose tapering if necessary for subject safety). Protocol-required procedures for study discontinuation and follow-up must be performed on the subject unless contraindicated by pregnancy (eg, x-ray studies). Other appropriate pregnancy follow-up procedures should be considered if indicated.

The investigator must immediately notify the BMS Medical Monitor (or designee) of this event and complete and forward a Pregnancy Surveillance Form to BMS (or designee) within 24 hours and in accordance with SAE reporting procedures described in [Section 6.1.1](#).

Follow-up information regarding the course of the pregnancy, including perinatal and neonatal outcome and, where applicable, offspring information must be reported on the Pregnancy Surveillance Form.

Any pregnancy that occurs in a female partner of a male study participant should be reported to the sponsor. Information on this pregnancy will be collected on the Pregnancy Surveillance Form.

6.5 Overdose

An overdose is defined as the accidental or intentional administration of any dose of a product that is considered both excessive and medically important. All occurrences of overdose must be reported as an SAE (see Section 6.1.1 for reporting details.).

6.6 Potential Drug Induced Liver Injury

Wherever possible, timely confirmation of initial liver-related laboratory abnormalities should occur prior to the reporting of a potential DILI event. All occurrences of potential DILIs, meeting the defined criteria, must be reported as SAEs (See Section 6.1.1. for reporting details).

Potential DILI is defined as:

1. AT (ALT or AST) elevation > 3 times upper limit of normal (ULN)

AND

2. Total bilirubin > 2 times ULN, without initial findings of cholestasis (elevated serum alkaline phosphatase),

AND

3. No other immediately apparent possible causes of AT elevation and hyperbilirubinemia, including, but not limited to, viral hepatitis, pre-existing chronic or acute liver disease, or the administration of other drug(s) known to be hepatotoxic.

6.7 Other Safety Considerations

Any significant worsening noted during interim or final physical examinations, electrocardiograms, x-rays, and any other potential safety assessments, whether or not these

procedures are required by the protocol, should also be recorded as a nonserious or serious AE, as appropriate, and reported accordingly.

Second primary malignancies (SPMs) will be collected throughout the study which includes assessments during survival follow-up. All SPMs that occur during the screening period and within 60 days of discontinuation of dosing will be reported as an SAE regardless of relationship to study drug. Additionally, any SPM that occurs after this timeframe and considered related to study drug will be reported as an SAE. All other SPMs will be collected and reported as adverse events.

7 DATA MONITORING COMMITTEE AND OTHER EXTERNAL COMMITTEES

A data monitoring committee (DMC) will be established before the first subject is treated and will monitor safety throughout the study. (The DMC will receive SAE tables every 4 months and more comprehensive safety data every 8 months.) In addition, the DMC will review safety and efficacy data, including a formal comparison of PFS for early stopping, once the following two conditions have been met: at least 338 progression events have been observed and all subjects have been randomized. A separate charter will describe the activities of this committee. (Also see [Section 8.5](#), Interim Analyses, for details on the interim analyses of safety and efficacy).

8 STATISTICAL CONSIDERATIONS

8.1 Sample Size Determination

The number of events and power for PFS were calculated assuming an exponential distribution in each arm. One interim analysis of PFS is planned. The comparisons of PFS will be carried out using log-rank tests stratified by stage of disease (International Staging System 1 - 2 versus 3), ECOG performance status (0 versus 1 - 2), and age (< 75 years old versus \geq 75 years old). The interim analysis will allow for early stopping for superiority. An O'Brien and Fleming α spending function will be employed to determine the stopping boundaries.

Approximately 750 subjects will be randomized to the 2 treatment groups in a 1 to 1 ratio in order to obtain at least 482 progression events, ie, documented progressions or deaths as determined by the IRC. Four hundred and eighty-two (482) events ensure that a two-sided, 5% level, sequential test procedure with 1 interim analysis after 70% of the total events (338) will have 90.5% power if the median PFS times in the control and experimental arms are 25 and 33.75 months, respectively, ie, if the hazard ratio of the experimental to control arm is 0.74. Assuming an accrual rate of 24 subjects per month, it will take approximately 60 months to obtain the required number of events, 31 months for accrual and 29 months for PFS follow-up. It is projected that at the time of final PFS analysis (at least 482 events), an observed hazard ratio of 0.84 or less, which corresponds to a 4.8 month or greater improvement in median PFS (25 vs 29.8 months), would result in a statistically significant improvement in PFS for the elotuzumab-containing arm. In view of evolving results with frontline lenalidomide therapy, a reassessment of the sample size could be made. The decision to reevaluate sample size would be based on external data only and would not involve a change in the required number of PFS events.

Survival, a key secondary endpoint, will be compared between the two arms at the time of the interim analysis of PFS (if and only if both PFS and ORR are positive), and again after 354 deaths, which is projected to occur 7 years (84 months) after the initiation of the study. An O'Brien and Fleming α -spending function will be used to obtain the nominal significance levels for the interim and final analyses of survival. Three hundred and fifty-four (354) deaths ensure that a two-sided 5% level sequential test procedure with one interim analysis will have 80% power for a 8.7 percentage point improvement in 4-year survival rate from 59.0%³⁶ to 67.7%, ie, for a HR = 0.74.

Power calculations were done using East v5.1.

8.2 Populations for Analyses

The following subject populations will be used in this study:

- Randomized subjects: all subjects who were randomized to either treatment group
- Treated subjects: all randomized subjects who received at least one dose of study treatment

Analyses of baseline characteristics, including demography, patient-reported outcomes, and efficacy will be carried out on all randomized subjects. Analyses of safety will be based on all treated subjects.

8.3 Endpoint Definitions

8.3.1 Progression-Free Survival

The primary definition of progression-free survival (PFS) is the time from randomization to the date of the first documented tumor progression, using the criteria in [Section 5.4.5.5](#), or to death due to any cause, provided death does not occur more than 10 weeks (2 or more assessment visits) after the last tumor assessment. Clinical deterioration will not be considered progression.

The following censoring rules will be applied for PFS:

- Subjects who receive systemic secondary anti-myeloma therapy prior to documented progression will be censored on the date of the last tumor assessment prior to the initiation of the new therapy.
- Subjects who have an event (documented progression or death) > 10 weeks (2 assessment visits) after the last prior tumor assessment will be censored at the last prior assessment.
- Subjects who do not progress and who do not receive subsequent therapy will be censored at their last tumor assessment.

The main analysis of PFS will be by IRC assessments.

IRC PFS also will be analyzed applying an intent-to-treat (ITT) definition that utilizes all data on each randomly assigned subject until either a progression event or the end of the study. PFS under the ITT definition will be defined as the time from randomization to the date of the first documented tumor progression or to death due to any cause. Clinical deterioration will not be considered progression. Subjects who neither progress nor die will be censored on the date of

their last tumor assessment. There will be no censoring for subsequent therapy prior to progression or for progression events following missing assessments.

Finally, PFS based on investigator assessments will also be analyzed applying both the primary and the ITT definitions.

8.3.2 Objective Response Rate

Best overall response is determined as the best assessment based on all study efficacy data for the subject. Subjects with objective response are subjects with a best overall response on study of partial response (PR) or better based on criteria in [Section 5.4.5](#).

Objective Response Rate (ORR) is defined as the proportion of subjects with objective response among all randomized subjects. The main ORR analysis will be based on IRC assessments.

[REDACTED]

[REDACTED]

[REDACTED]

8.3.6 Survival

Survival is defined as the time from randomization to the date of death. A subject who has not died will have his or her survival duration censored at the date of last contact (“last known date alive”).

[REDACTED]

8.4 Analyses

8.4.1 Demographics and Baseline Characteristics

Subject characteristics including demographics, baseline performance status, disease characteristics, and baseline laboratory parameters will be summarized by randomized treatment arm as well as pooled across randomized arms using descriptive statistics.

8.4.2 Efficacy Analyses

8.4.2.1 Primary Efficacy Analysis

The primary endpoint for the study is progression-free survival based on IRC assessment. The primary analysis of PFS will be to compare the 2 randomized arms at the interim and final looks via two-sided, log-rank tests stratified by stage of disease (International Staging System 1 - 2 versus 3), ECOG performance status (0 versus 1 - 2), and age (< 75 years old versus \geq 75 years old). An O'Brien-Fleming α spending function will be employed to determine the significance levels and stopping boundaries at the interim and final looks. (See [Section 8.5](#), Interim Analysis, for more detail).

Further analysis of PFS will include the computation of hazard ratios and estimation of PFS functions. The PFS hazard ratio of lenalidomide/dexamethasone + elotuzumab to lenalidomide/dexamethasone alone and an associated two-sided confidence interval will be computed using a stratified Cox proportional hazards model with treatment arm as the sole covariate. The alpha level (α) for the confidence interval will be the same as the nominal significance level for the hypothesis testing. The stratification factors will be the same as those used in the randomization. The PFS functions for each randomized arm will be estimated using the Kaplan-Meier product-limit method. Two-sided, 95% confidence intervals for median PFS and the first and third quartiles will be computed by randomized arm.

[REDACTED]

8.4.2.3 Secondary Efficacy Analyses

The key secondary endpoints are:

- Objective response rate (ORR)
- Overall survival

A hierarchical procedure will be used to ensure a two-sided, family-wise type I error rate of 5% for testing the one primary and two key secondary endpoints. If there is a statistically significant improvement in PFS, ORR will be compared between arms at the 5% level. If the comparison of ORR is also statistically significant at the 5% level, then survival will be compared between arms using a 5% level sequential test procedure.

Objective response will be compared between randomized arms using a two-sided 5% level Cochran-Mantel Haenszel (CMH) test stratified by the same factors used in the analysis of PFS. An associated odds ratio and 95% confidence interval will be calculated. The response rate and its corresponding 95% confidence interval will also be calculated for each treatment arm. There will be no interim comparison of this endpoint.

Survival will be compared between treatment arms using two-sided, stratified log-rank tests at the interim and final looks. The family-wise type I error rate for the sequential testing procedure will be 5% and the stratification factors will be the same as those used for the randomization. The significance level at the interim and final analyses of survival will be determined using an O'Brien and Fleming α spending function.

Other Secondary objectives are:

- Change from baseline of mean score of pain severity and change from baseline of mean score of pain interference (BPI-SF)

Each of the two comparisons will be made at the two-sided type I error of 2.5% and will be tested independent of the significance of the comparison of the progression-free survival, objective response rate and overall survival. See [Section 8.4.7.1](#) for details about analyses.

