The key secondary endpoints are:

- Objective response rate
- Overall survival

Objective response rate (ORR) is defined as the proportion of randomized subjects who have a best overall response of partial response or better. Overall survival is the time from randomization until death. Subjects who do not die will be censored at the date of last contact.

A hierarchical procedure will be used to ensure a two sided family-wise type I error rate of 5% for testing the one primary and two key secondary endpoints. If there is a statistically significant improvement in PFS, then ORR will be compared between arms at the two-sided 5% level. If the comparison of ORR is also statistically significant, then survival will be compared between arms using a two-sided 5% level sequential test procedure.

Objective response rate will be compared between randomized arms using a two-sided 5% level Cochran-Mantel Haenszel (CMH) test stratified by the same factors used in the analysis of PFS. An associated odds ratio and 95% confidence interval will be calculated. The response rate and its corresponding 95% confidence interval will also be calculated for each treatment arm. There will be no interim comparison of this endpoint.

Survival will be compared between treatment arms using two-sided, stratified log-rank tests at the interim and final looks. The family-wise type I error rate for the sequential testing procedure will be 5% and the stratification factors will be the same as those used for the randomization. The significance level at the interim and final analyses of survival will be determined using an O'Brien and Fleming α spending function.

Other Secondary endpoints include change from baseline in mean score of pain severity and mean score of pain interference using the BPI-SF. The two endpoints will be tested at the 2-sided 2.5% level each and will not be part of the hierarchical testing procedure. For these two endpoints, comparison will be conducted using a longitudinal mixed model with treatment arm and time point (categorical) and baseline score as fixed effects and a banded covariance matrix (covariances are constant on each diagonal of the matrix).

TABLE OF CONTENTS

TITLE PAGE 1

DOCUMENT HISTORY 3

SYNOPSIS 5

TABLE OF CONTENTS 9

1 INTRODUCTION AND STUDY RATIONALE 13

[REDACTED] [REDACTED]

1.2 Research Hypothesis 14

1.3 Objectives 15

 1.3.1 Primary Objective 15

 1.3.2 Secondary Objectives 15

[REDACTED] [REDACTED]

2 ETHICAL CONSIDERATIONS 34

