8.4.7 Outcomes Research Analyses

8.4.7.1 Analysis of HRQoL Data

All analyses will be conducted on randomized subjects. Questionnaire completion rate, defined as the proportion of questionnaires actually received out of the expected number (ie, the number of subjects still on treatment), will be calculated and summarized at each assessment point. Subjects without any post-baseline assessment will be excluded from the analysis.

The comparison between the 2 treatment arms of the change from baseline in the mean score of pain severity will be conducted using a longitudinal mixed model with treatment arm, time point (categorical), and baseline score as fixed effects and a banded covariance matrix (constant covariances on each diagonal of the matrix). Similar model will be used to analyze change from baseline in mean score of pain interference.

Adjusted mean change from baseline at each assessment point will be graphically presented by randomized arm for the three questionnaires [REDACTED] and BPI-SF).

[REDACTED]

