7.5 Efficacy

Efficacy analyses (PFS, ORR and OS) will be conducted on the population of all randomized subjects, grouped by arm assigned at randomization, unless otherwise noted.

The main analyses of PFS and ORR will be based on IRC evaluation. Unless stated otherwise, whenever a stratified analysis is specified, the stratifications factors will be those used in the randomization (per IVRS), that is:

- Stage of disease (ISS 1 – 2 versus 3)
- Age (< 75 years old versus \geq 75 years old)
- ECOG Performance status (0 versus 1 - 2)

All p-values reported will be two-sided. Confidence intervals (CI) for the PFS and OS endpoints will be based on the nominal significance level adjusted for the interim analyses to preserve the overall type I error rate. Two-sided 95% CI will also be provided. CIs for the other endpoints will be at the two-sided 95% level. The p-values presented in the clinical study report will be rounded to the fourth decimal place. Point estimates and confidence bounds for efficacy variables will be rounded to the second decimal place.

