7.5.11 Hierarchy for Testing Secondary Endpoints

A hierarchical procedure will be used to preserve a two-sided family-wise type I error rate of 5% for testing one primary (PFS) and two key secondary endpoints (ORR and OS) in this study.

If there is a statistically significant improvement in PFS, ORR will be compared between treatment arms at the two-sided 5% alpha level. If, and only if, the comparison of ORR is statistically significant, then OS will be compared between treatment arms using a 5% sequential test procedure.

The two QOL secondary endpoints will not be part of the hierarchical testing and will be tested independently of the significance of the other endpoints. Each of the two comparisons will be made at the two-sided type I error of 2.5%.

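### Minor improvement: the two BPI-SF pain endpoints are fixed at 2.5% each, where a Holm step-down would keep the same implied 5% bound and never reject less

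*Protocol*

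**What the plan says.** Three places set the rule, and they agree.

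- Protocol synopsis, endpoint definitions and analyses: "The two endpoints will be tested at the 2-sided 2.5% level each and will not be part of the hierarchical testing procedure".
- Protocol 8.4.2.3: "Each of the two comparisons will be made at the two-sided type I error of 2.5" per cent, whatever PFS, ORR and OS show.
- SAP 7.5.11 gives the same level and says that the two comparisons "will be tested independently of the significance of the other endpoints".

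Each endpoint has one treatment comparison, from a "longitudinal mixed model with treatment arm, time point (categorical), and baseline score as fixed effects" (Protocol 8.4.7.1). The stated overall control, a "family-wise type I error rate of 5% for testing the one primary and two key secondary endpoints", covers PFS, ORR and OS only. No level is stated for the pain pair as a pair. No visible text lets one pain endpoint's level pass to the other.

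**The concern.** Halving the level for each of two tests has one obvious purpose, which is to hold the pair at 5%. If so, the fixed split is stricter than it needs to be in one situation: one pain endpoint is significant at 2.5% and the other has a p-value above 0.025 and at or below 0.05. The plan then declares the second endpoint not significant, although a 5% bound for the pair does not require that.

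The situation is realistic. Both scores come from one questionnaire completed at the same visits, so a clear result on one beside a borderline result on the other could well occur. At stake is the second claim in a comparison that both documents list as a secondary objective. PFS, ORR and OS are not affected.

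**Working it through.** **Inputs from the documents.** Two endpoints; two-sided 2.5% each; no exchange of level with the PFS-ORR-OS hierarchy.

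**Inputs assumed.** Effect size, power and correlation, because the documents give none for BPI-SF. I take equal true effects on both endpoints and bivariate normal test statistics with correlation r.

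**1. The plan's own level.** 2 × 0.025 = 0.050, an equal Bonferroni split. If the two tests were independent, the pair's error would be 1 − 0.975² = 0.0494.

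**2. Holm keeps the same bound.** The rule: test the smaller p at 0.025; if it is rejected, test the other at 0.05.

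- Both nulls true: any false rejection needs the smaller p ≤ 0.025, which has probability at most 0.025 + 0.025 = 0.05. This is the same event as under the fixed split, so the error is identical. Simulation (4 million pairs) gave 0.0493 at r = 0, 0.0429 at r = 0.7 and 0.0361 at r = 0.9 for both rules.
- One null true: a false rejection needs that endpoint's p ≤ 0.05, so the error is at most 0.05. With the other endpoint at 80% power, simulation gave 0.0449 (r = 0) falling to 0.0377 (r = 0.9).

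Neither argument uses the correlation.

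**3. Size of the gain.** Critical values are 2.241 (2.5%) and 1.960 (5%). The common mean of the two statistics is 2.241 + z(power), where power is per endpoint at the 2.5% level. Write

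- B = P(Z1 > 2.241 and Z2 > 2.241)
- X = P(Z1 > 2.241 and Z2 > 1.960)

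The fixed split wins both with probability B. Holm wins both with probability 2X − B. A given endpoint moves from its power to power + (X − B), so the per-endpoint gain is half the gain in winning both.

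Example, 80% power and r = 0.7: mean = 2.241 + 0.842 = 3.083, B = 0.7129, X = 0.7536.

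- Both won: 71.3% rises to 2 × 0.7536 − 0.7129 = 79.4%.
- A given endpoint: 80% rises to 0.80 + 0.7536 − 0.7129 = 84.1%.
- At least one: 0.80 + 0.80 − 0.7129 = 88.7% under either rule.

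Gain in the chance of winning both, in percentage points:

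| Power at 2.5% | r = 0.5 | r = 0.7 | r = 0.8 |
|---|---|---|---|
| 50% | 10.4 | 9.9 | 9.5 |
| 60% | 10.9 | 10.1 | 9.5 |
| 70% | 10.6 | 9.6 | 8.9 |
| 80% | 9.1 | 8.1 | 7.5 |
| 90% | 6.1 | 5.4 | 4.9 |

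The range is 4.9 to 10.9 points for both, so 4.9/2 ≈ 2.5 to 10.9/2 ≈ 5.5 points for a given endpoint. Outside this grid the gain can be smaller: at 10% power and r = 0.7 it is about 3 points for both.

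**4. On the trial's scale (illustration).** Protocol 8.1 plans about 750 subjects, so about 375 per arm. Treat each endpoint as a simple comparison of two means, with r = 0.5 and an assumed standardized effect on both. The chance of winning both rises from 54.5% to 65.2% (effect 0.20), from 80.4% to 87.3% (0.25) and from 94.4% to 97.0% (0.30).

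**The case against.** The strongest reply is that nothing here is wrong. The fixed split is valid, prespecified and identical in three places, and no conclusion drawn under it would be false. That stands, and it makes the point minor.

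The fixed split also has real advantages. Neither test depends on the other, and each pairs with a simple 97.5% interval. It holds each endpoint's own false-positive rate at 2.5% even when the other endpoint has a true effect. Under Holm that rate rises to about 3.8-4.5% in the simulations above, though still within 5%. A sponsor may reasonably prefer these properties, and they should be weighed against the power.

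The power figures rest wholly on assumptions. If only one endpoint has a true effect there is almost nothing to gain, and if neither has, there is nothing.

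Three stronger readings are tempting, and the documents do not support them.

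- *The SAP's interval rule contradicts the 2.5% test.* SAP 7.5 says "CIs for the other endpoints will be at the two-sided 95% level", and a 95% interval could exclude zero beside a pain test that failed at 2.5%. But that section opens by scoping efficacy analyses to PFS, ORR and OS, so the other endpoint there is most naturally ORR. The visible SAP has no section on BPI-SF analysis, and redacted text may hold one. No contradiction can be charged to the plan.
- *Adding 97.5% intervals would align interval and test.* Under Holm it would not. With p-values 0.01 and 0.04 both endpoints are significant, yet the second 97.5% interval includes zero. With a smaller p of 0.03 neither is significant, yet that endpoint's 95% interval excludes zero. No single interval level matches the step-down in every case.
- *The plan exceeds its promised 5%.* The promise covers PFS, ORR and OS only. Adding the separate pain pair gives a bound of 0.05 + 0.05 = 0.10 across all five endpoints, and Holm leaves that bound as it is.

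**Conclusion.** The point holds as a cheap, minor improvement. The current rule is a valid Bonferroni split, and Holm dominates it in rejections at the same bound for the pair. That conclusion needs no assumption about correlation or effect size. It does assume that 5% for the pair is the intended bound, which follows from 2 × 2.5% and is not stated.

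The stated gains of about 5 to 11 points for both endpoints and 2.5 to 5.5 points for a given endpoint are conditional on equal real effects, 50-90% power and correlation 0.5-0.8. More power here means more chance of the second claim. A reader should not infer a better chance of at least one significant result.

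**What to change.** In the synopsis, Protocol 8.4.2.3 and SAP 7.5.11, replace the fixed-level sentence with this rule: test the smaller of the two BPI-SF p-values at two-sided 2.5%; if it is significant, test the other at two-sided 5%; otherwise declare neither significant. Say that this holds the pair at 5% and leaves the PFS-ORR-OS hierarchy untouched.

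Add that confidence intervals for the two pain endpoints are unadjusted, and that significance is decided by the step-down procedure.

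Make the change before BPI-SF data are unblinded. The trial is open-label, but SAP 2.3 keeps the randomization codes from the study team, so this condition can be met and documented.

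The cost is a few lines of wording in two documents, with no added data or subjects and no change in the pair's error bound. The exact match between each test and a simple 97.5% interval is lost.
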